Total body muscle mass will be assessed directly by the D₃-creatine dilution method (27). Low muscle mass measured by this method has been associated with slower walking speed, lower SPPB score, and more falls in older men (27). The D₃-creatine dilution method involves a participant ingesting a capsule containing the 60-mg dose of stable isotope-labeled creatine (D₃-creatine), and then providing a fasting morning urine sample 72–144 hours (3–6 days) later. To minimize variability in this muscle mass measurement, participants will be asked not to eat foods containing creatine or creatinine (animal products) after their mid-day meal on the day prior to these urine collections on visits 0 and 12 months. A handout will be provided to guide participants in what they should and should not eat on these two occasions. Urine D₃-creatinine, unlabeled creatinine, and creatine are measured using high performance liquid chromatography and tandem mass spectroscopy; these measures are then included in an algorithm to determine total body creatine pool size and thus skeletal muscle mass (39). The doses will be prepared by Greenpark Pharmaceuticals in Houston, TX. The urine samples will be de-identified and sent to [name] laboratory at U.C. Berkeley for analysis. [name] will be blinded to treatment group and sequence (baseline, 12 mo) during the analyses.

Biochemical measurements

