Secondary aims - With 4 measurements (baseline, 2, 6, and 12 months), we will test whether the change over time is linear with use of linear models with random effects. The observed pattern of change in ALM over time will give an indication of the potential long-term benefit (or lack thereof) of anamorelin treatment. A significance level of 0.05 will be used.

The findings from secondary (and exploratory) analyses will be used for hypothesis generation, rather than to draw conclusions.

Exploratory aims – Exploratory outcomes will be analyzed as described above. For those with more than two measurements, the pattern of change will be analyzed as described above for ALM.

The primary analyses will follow intention-to-treat principles. The intent to treat population will include all subjects who had 1 or more visits after visit 0 (baseline). We will also perform per protocol analyses, in which subjects who develop clinical conditions during the study that influence the study outcomes (i.e., started treatment on an osteoporosis drug or glucocorticoids) or with selected protocol deviations will be excluded. Data will be diagnosed to evaluate validity of model assumptions. Assumptions of normality and homoscedasticity will be evaluated in these models and appropriate variable transformations will be applied if needed to satisfy model assumptions. If model assumptions do not hold for the linear mixed models, robust standard errors will be used. An exploratory per-protocol analysis will also be performed.

Safety and tolerability measures will be summarized for each treatment group based on clinical symptoms and circulating levels of glucose and ALT/AST. Adherence will be assessed by intake diary and pill counts.

K. Withdrawal from the study

Participants can go permanently “off study” only for withdrawal of consent, defined as no longer wishing to participate in all aspects of the trial. The PI may also withdraw participants for safety reasons. Participants can be off of study pills (non-adherent) but remain in the study and return for scheduled follow-up visits. Participants who are instructed by their doctor to gain weight during the study will not be withdrawn from the study.

PROTECTION OF HUMAN SUBJECTS

a. Materials and potential risks

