Research material will include records made of the response to prescreening questionnaires, medical history, height, weight, blood pressure, and DXA scans on the screening visit. During the study, additional data in the form of records from study visits, responses to questionnaires and testing procedures will be obtained as described above.

b. Known potential risks to subjects

Anamorelin has the potential to cause hyperglycemia. In the two Phase 3 trials, hyperglycemia grade 1-2 (requiring treatment with diet modification or an oral agent) occurred in 5% (vs 3% in placebo) in one trial and 3% (vs <1% in placebo) in the other trial (26). Grade 3 hyperglycemia (requiring insulin) occurred in ≤ 1% of anamorelin and placebo users in both trials. Patients with uncontrolled diabetes (defined as fasting glucose ≥200 mg/dl) were excluded from participating in the published Phase 3 trials. In the 12-wk safety extension period, the incidence of drug-related AEs declined (29). Hyperglycemia occurred in 1.2% in the anamorelin group compared with none in the placebo group.

Anamorelin has the potential to cause gastrointestinal symptoms. In the two 12-wk Phase 3 trials, mild to moderate gastrointestinal complaints occurred in 6% (vs 2% in placebo) in one trial and 2% (versus <1% in placebo) in the other (26). Of the gastrointestinal complaints, nausea accounted for half to two thirds of the complaints, constipation one quarter, and vomiting 0 to one quarter. In one of the trials there were no severe gastrointestinal adverse events and in the other, severe nausea and vomiting occurred in <1% (26). In the 12-wk safety extension, nausea occurred in 0.6% of the anamorelin group, compared with 0 in the placebo group, indicating that anamorelin is suitable for long-term use (29). The risk of gastrointestinal symptoms occurring in our study subjects may be lower than in the stage 4 lung cancer patients who were often also receiving cancer treatments, but this is unknown.

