DXA scans will be performed by DXA technicians who are experienced and certified by International Society for Clinical Densitometry and the State of MA. Should a participant's BMD of the spine or hip decline by >7% on 2 consecutive measurements, the participant will be notified and referred to his/her PCP. The participant will remain in the study.

The muscle performance measurements will be administered by an experienced research coordinator who will observe the subject during testing.

Because of the potential of anamorelin to increase fasting plasma glucose, we will monitor glucose on each visit. If it is elevated (≥ 200 mg/dl), we will repeat the measurement. If again elevated ≥ 200 mg/dl, the study pills will be discontinued. Discontinuation of study pills will be managed without unblinding the study team, and those participants will continue with study measurements (for the intent-to-treat analysis). Subjects will be asked to consume their usual dinner on the evening prior to each study visit.

Sporadic, mild increases in serum AST/ALT have been observed in subjects on anamorelin. We will monitor AST/ALT on each study visit and discontinue use of anamorelin if these levels exceed 2x the upper end of the reference range (>74 and >68 MU/ml, respectively) on repeat measurement.

In order for participants to achieve therapeutic levels of anamorelin, we will exclude subjects on CYP3A4 inducers which may increase the metabolism of anamorelin (e.g., rifampin). We will also have participants take study pills 1 hour before breakfast, as food reduces anamorelin bioavailability.

To minimize risk that anamorelin levels become supra-therapeutic, we will: a) instruct participants never to take more than one study pill per day (that is, not to 'catch up' after missing a dose); b) exclude participants taking strong CYP3A4 inhibitors (ketoconazole, clarithromycin, itraconazole, nefazodone, telithromycin); c) exclude participants taking drugs with high binding affinity to AAG because they have the potential to displace anamorelin from binding (e.g., carvedilol, chlorpromazine); d) exclude participants taking inhibitors of P-glycoprotein (e.g., verapamil, quinidine), and e) inhibitors of OATP1B3 (e.g., cyclosporine, rifampicin)

We will instruct participants to notify [name] of any new prescriptions (before taking the first dose) and of any changes in health status or of any hospitalizations or emergency room visits.

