Nonclinical data indicate that the T_{max} in cardiac tissue is delayed compared with plasma T_{max} (4 hrs vs 1 hr, respectively). We will perform a screening ECG and exclude individuals with clinically meaningful abnormalities. We will also perform ECGs before and 1 and 4 hrs after the first dose of the study pills.

Stopping rules

- We will discontinue the subject's participation in the study if the QT interval exceeds 470 ms or if other clinically meaningful ECG changes occur at either 1 hr or 4-hrs post first dose (4 hrs post dose is the time when the anamorelin concentration in cardiac tissue is maximal).
- We will discontinue the subject's participation in the study in the event that he/she develops cardiac symptoms (e.g., chest pain, chest pressure, palpitations) or evidence of significant fluid retention (peripheral edema, pulmonary congestion).
- We will discontinue a subject's participation in the study if he/she is prescribed the following drugs during the study:
 - CYP3A4 inhibitor (ketoconazole, clarithromycin, itraconazole, nefazodone, or telithromycin)
 - Channel blocking antiarrhythmic medication (flecainide, procainamide, propafenone, quinidine)
 - Drugs with high affinity to AAG (carvedilol, chlorpromazine)
 - Inhibitors of P-glycoprotein (verapamil, quinidine)
 - Inhibitors of OATP1B3 (cyclosporine, rifampicin)
- We will discontinue a subject's participation in the study if he/she develops glycemia defined as fasting plasma glucose ≥ 200 mg/dl on two consecutive measures.

Subjects developing these findings or symptoms will be referred to their physicians and these adverse events will be recorded and reported to the IRB, the NIH, and Helsinn Therapeutics. The study physician will follow up with the subject and his/her physician until symptoms have been appropriately addressed.

We will exclude subjects with eGFR < 30 ml/min.

The study will be approved by the Tufts IRB before anyone will be recruited for the study. All study personnel have been certified by the Tufts IRB to work with clinical research participants. All research activity will take place at the HNRCA. Written informed consent will be obtained from each participant.

The PI will inform the IRB of any updated information that may affect the conduct of this study or subject safety, rights, welfare or willingness to take part in the research.

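### Two sections give conflicting orders for confirmed fasting glucose of 200 mg/dl or more, and one of them forfeits the only post-baseline primary measurement

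*Combined protocol and SAP*

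**What the plan says.** Four parts of the protocol bear on this event.

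- **Protection against risks.** A glucose of 200 mg/dl or more is repeated. If the repeat is also 200 or more, the pills stop without unblinding the team, and "those participants will continue with study measurements (for the intent-to-treat analysis").
- **Stopping rules.** The investigators will "discontinue a subject's participation in the study if he/she develops glycemia defined as fasting plasma glucose" of 200 mg/dl or more on two measurements in a row.
- **Section K, Withdrawal from the study.** Participants leave the study permanently "only for withdrawal of consent, defined as no longer wishing to participate in all aspects of the trial". The next sentence adds: "The PI may also withdraw participants for safety reasons". The one after that says: "Participants can be off of study pills (non-adherent) but remain in the study and return for scheduled follow-up visits".
- **Section J, Data analysis.** The primary analysis is a two-sample t-test on 12-month change, under intention-to-treat principles. "The intent to treat population will include all subjects who had 1 or more visits after visit 0 (baseline"). No method is given for a missing month-12 value.

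The primary outcome rests on "urine collections on visits 0 and 12 months" (section F, D₃-creatine). The schedule in section B shows no other collection, and no early-termination sample is described. Glucose is checked at months 2, 6 and 12.

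**The concern.** Analyte, threshold and confirmation by a second value are the same in both rules, but the required actions differ, and no section says which rule prevails.

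The choice matters because the primary outcome has a single post-baseline value. P1NP and DXA lean mass are also measured at months 2 and 6, so values up to the trigger visit are kept. D₃-creatine has nothing to keep. A subject removed at month 2 or 6 has attended a post-baseline visit and so belongs to the intention-to-treat population, yet has no 12-month change to analyse. An event first found at month 12 costs nothing.

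The loss may also be related to treatment. The protocol names raised glucose as a potential drug effect. For the earlier 12-week safety extension it reports: "Hyperglycemia occurred in 1.2% in the anamorelin group compared with none in the placebo group".

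**Working it through.** **1. The two rules side by side**

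| | Protection against risks | Stopping rules |
|---|---|---|
| Trigger | 200 mg/dl or more, confirmed on repeat | 200 mg/dl or more, two in a row |
| Pills | stop | stop (participation ends) |
| Scheduled measurements | continue | end |
| Month-12 D₃-creatine | obtained | lost if triggered at month 2 or 6 |

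If two in a row is read as two scheduled visits, the Stopping rules act later, but they still end measurements that the other section says will continue. Nor can participation simply mean pills: section K treats being off pills and being off study as different states.

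**2. The plan's own sample-size figure**

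Inputs from section I: SD of change 1.84 kg, 12 completers per group, minimal detectable difference below 2.28 kg. Power for the primary endpoint is not stated, so I assume 80%, with two-sided alpha 0.05. With the noncentral t distribution, the minimal detectable difference is 2.20 kg at 12 per group and 2.31 kg at 11. The statement reproduces, and 12 is the smallest number that satisfies it.

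Power at 2.28 kg is 82.7% with 12 vs 12, 80.8% with 12 vs 11, and 78.6% with 12 vs 10.

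**3. How often it might happen**

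The rate of confirmed glucose of 200 or more over 12 months is not given. The risk section reports, for anamorelin, grade 3 hyperglycemia of at most 1% in the main trials (also at most 1% on placebo), 1.2% in the extension, and grade 1-2 rates of 3% and 5% in the two main trials (placebo below 1% and 3%). None of these is a rate at this threshold, so I take 1% to 5% as an assumption. With 16 anamorelin subjects (32 randomized 1:1), expected events are 16p and P(at least one) = 1 − (1 − p)^16.

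| p | Expected events | P(at least one) |
|---|---|---|
| 1% | 0.16 | 15% |
| 1.2% | 0.19 | 18% |
| 3% | 0.48 | 39% |
| 5% | 0.80 | 56% |

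This trial's tighter glucose and diabetes exclusions could lower these rates; its 12-month treatment, against 12-week trial periods, could raise them.

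**4. What one removal does to the estimate**

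Let g be the removed subject's unmeasured month-12 benefit over placebo, and n the number per arm had that subject been followed. The true difference is ((n − 1) × 2.28 + g)/n. The analysis without the subject gives 2.28, so the error is (2.28 − g)/n. The standard error is 1.84 × √(2/n): 0.65 kg at n = 16 and 0.75 kg at n = 12.

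| Assumption about the removed subject | g (kg) | Error, n = 16 | Error, n = 12 |
|---|---|---|---|
| Average responder | 2.28 | 0 | 0 |
| Stopped at month 6, gain kept (2.28 × 6/12) | 1.14 | +0.07 kg | +0.10 kg |
| Stopped at month 2, gain kept (2.28 × 2/12) | 0.38 | +0.12 kg | +0.16 kg |
| All benefit lost | 0 | +0.14 kg (0.22 SE) | +0.19 kg (0.25 SE) |
| 1 SD above average (2.28 + 1.84) | 4.12 | −0.12 kg | −0.15 kg |

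A plus sign means the treatment difference is overstated. The error can take either sign. The rows are not limits: a subject could finish below the placebo mean, or more than 1 SD above the average response.

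**The case against.** The strongest reply is that this is a wording slip of little consequence. Most likely zero or one subject is affected. Section A already allows 32 enrolled to fall to 24 completers, so one or two losses can be absorbed. The study is a single-site pilot in which one investigator oversees all activity, so inconsistent handling is unlikely. The text also leans one way: the Protection against risks section alone addresses study measurements after a glucose stop, it gives the intention-to-treat reason, and section K agrees with it. All of this stands, and it limits the weight of the point.

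It does not remove the conflict. Section K lets the investigator withdraw someone for safety, and the later Withdrawal paragraph allows participation to be ended at any time to protect the subject. Those powers are discretionary. They do not reconcile one rule that requires continued measurement with another that requires removal.

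A reader might infer more than the documents support:

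- **That the conflict biases the trial in favour of anamorelin.** No direction is established. The risk section links outsized fat gain to higher glucose, but also says that gains in fat alone have not been seen with the drug.
- **That removed subjects lose safety care.** The Stopping rules keep the study physician involved until symptoms are dealt with. Only scheduled study measurements are lost.
- **That the whole stopping list is contradictory.** The ECG, cardiac, fluid-retention and drug triggers also end participation, but only the glucose trigger has a second, specific instruction elsewhere.

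**Conclusion.** The conflict is certain from the text; its expected effect is small. Following the Stopping rules after a month-2 or month-6 trigger gives up that subject's only post-baseline primary value, for a reason that may be drug-related, although pills stop under either rule.

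The calculated range rests on an assumed 1% to 5% event rate, the protocol's 2.28 kg and 1.84 kg, and one affected anamorelin subject. If that subject would have lost all benefit, the overstatement is 0.14 to 0.19 kg. One fewer completer takes power from about 83% to 81%. This is an avoidable loss worth correcting, not a threat to the primary result.

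**What to change.** Replace the glucose bullet under Stopping rules with wording such as: *If fasting plasma glucose is 200 mg/dl or more on two consecutive measurements, we will stop the study pills, and the subject will stay in the study for all scheduled measurements, including month-12 D₃-creatine.* Leave the investigator's case-by-case safety withdrawal in place. A sentence in section J saying that month-12 values obtained off pills enter the primary comparison is optional, since section J and the Protection against risks section together already imply it.

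The cost is a minor protocol amendment, with IRB approval and the updated protocol sent to the FDA under the IND. There is no added drug exposure and there are no visits beyond the existing schedule, though a subject who would otherwise have left now continues with them. Including off-drug subjects slightly dilutes the on-drug effect. The planned per-protocol analysis can show that effect if its exclusions are defined to cover glucose stops.

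The change does not guarantee every month-12 value. Discretionary withdrawal remains, and 8 of 32 losses are already allowed for.

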ECGs before and 1 & 4 hr post dose		X					^e DXA total body scans at 2, 6, &12 mo; spine and non-dominant hip scans at 12 mo (screening scans will serve as baseline)
Diet assessment ^a		X				X	^f Serum P1NP at 0, 2, 6, and 12 mo; serum IGF-1 and CTX at 0 and 12 mo; serum 25(OH)D at 0 and mo 6; and alpha-acid glycoprotein at visit 0; archive 4 aliquots serum and 1 of plasma at 0 and 12 mo.
Questionnaires ^b		X		X		X	^g Safety monitoring: fasting plasma glucose & serum AST/ALT at 0, 2, 6, and 12 mo; symptoms and other AEs documented
Muscle strength ^c	X	X	X	X		X	^h By pill diary and counting returned pills
Muscle perform. ^d		X	X	X		X	ⁱ Administer 60-mg oral dose of D ₃ -creatine
DXA scans ^e			X	X		X	^j Collect fasting spot urine for D ₃ -creatine dilution determination
Study blood ^f		X	X	X		X	
Dispense pills		X	X	X			
Safety measures ^g		X	X	X		X	
Adherence ^h			X	X		X	
D ₃ -creatine dosing ⁱ	X				X		
Fasting spot urine ^j		X				X	
Waist circumference						X	

In addition to the above study visits, we will contact participants by telephone at 4, 8, and 10 months to determine whether they have any study related concerns and to remind them of the importance of taking one study pill per day. The content of these calls will be documented on the Call/comment Log.

C. Inclusion and exclusion criteria

Inclusion criteria: Ability to sign informed consent form; community dwelling men (who are sterile or agree to use contraception throughout the study) and postmenopausal women (no menses for 5 years; early postmenopausal women are ineligible because their bone turnover rate is changing rapidly); age 50 years and older; sarcopenia defined as maximum grip strength <35.5 kg (men) and <20 kg (women) in either hand (excluding hands with severe pain or recent surgery) and/or gait speed <0.8 m/sec (11); osteopenia defined as spine (at L1, L2, L3, or L4) or non-dominant total hip or femoral neck BMD T-score between -1.0 and -2.5; mini-mental state examination (MMSE) score >21.

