Blood will be drawn after a 12-hr overnight fast. Plasma glucose will be measured on an Olympus AU400 clinical chemistry analyzer with intra-assay CVs of 1%. IGF-1 will be measured by chemiluminescent immunoradiometric assay on an automated immunoassay system (IMMULITE 1000, Diagnostic Product Corp, LA, CA, USA) with CV of 3 – 9%. The biochemical markers of bone turnover, P1NP and CTX, were selected to assess bone formation and resorption because the International Osteoporosis Foundation and the International Federation of Clinical Chemistry and Laboratory Medicine have identified them as the most promising for clinical use (40). P1NP will be measured by competitive radioimmunoassay with RIA kits from Orion Diagnostica Uni®P1NP (Espoo, Finland) with intra- and inter-assay CVs of 5.0 and 8.1%, respectively. Serum CTX will be measured by an ELISA procedure, (Serum CrossLaps® ELISA, Immunodiagnostic Systems Inc., Fountain Hills, AZ) which employs monoclonal antibodies recognizing C-telopeptide fragments of collagen type I a1 chains containing the epitope Glu-Lys-Ala-His-Asp- $\ddot{\gamma}$ -Gly-Gly-Arg in an isomerized form, with CVs of 2-8%. IGF-1 will be measured by chemiluminescent immunoradiometric assay on an automated immunoassay system, (IMMULITE 1000, Diagnostic Product Corp., Los Angeles, CA) with a CV of 3%-9%. eGFR will be calculated by the MDRD equation (41). Alanine Aminotransferase (ALT) will be measured in serum by an enzymatic kinetic procedure on a clinical chemistry analyzer (AU480 Clinical Chemistry Analyzer, Beckman Coulter, Inc., Diagnostics Division Headquarters, Brea CA 92821.) The intra- and inter- assay CVs are 4.0% and 7.0% respectively. Aspartate aminotransferase (AST) will be measured in serum by an enzymatic kinetic procedure on a clinical chemistry analyzer, (AU480 Clinical Chemistry Analyzer, Beckman Coulter, Inc., Diagnostics Division Headquarters, Brea CA 92821. The intra- and inter- assay CVs are 3.8% and 6.6% respectively. Serum 25(OH)D will be assayed by LC/MS/MS with CV of a CV of 6% in an assay calibrated to NIST standards. Serum alpha-1acidglycoprotein (AGP) will be measured by an immuneturbidmetric procedure using the AU400 clinical chemistry analyzer (Beckman Coulter, Inc., Diagnostics Division Headquarters, [name]) as specified in the manufacturer's procedural documentation, with intra- and inter-assay C.V.s of 2.5% and 3.2% respectively.

G. Randomization

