Anamorelin may cause weight gain. Gains in lean mass and bone mass are the goal, thus weight gain is expected to occur. In a 12-week anamorelin trial in 174 lung cancer patients, anamorelin increased weight by 1.56 kg, in comparison with placebo and most of the gain occurred in the first 3 weeks of treatment (43). Fat mass is also expected to increase, but gains solely in fat mass have not been observed with anamorelin. To set a weight gain limit runs the risk of discontinuing those subjects who have the most favorable responses to treatment. Thus our approach is to set no weight limit but to monitor metabolic state which reflects the metabolic impact of the weight gain. Gains in lean mass are expected to improve glucose tolerance, whereas exclusive or outsized gains in fat mass would increase blood sugar. To address this and to minimize risk, we plan to exclude obese subjects and subjects taking insulin or sulfonylureas and those with fasting glucose levels on screening ≥ 150 mg/dl. To identify intra-study hyperglycemia we will monitor fasting plasma glucose at 2, 6, and 12 months.

Anamorelin at very high doses may lengthen the QT interval. A study in 60 normal adults (see Investigator brochure) revealed that a supra-therapeutic dose of 300 mg/d of anamorelin was associated with a small increase in heart rate as well as increases in the QT and PR intervals and QRS duration. *In contrast, data collected so far indicate that the therapeutic dose of anamorelin (100 mg) had no clinically meaningful effect on heart rate, QT or PR interval, or QRS duration.*

In conclusion, anamorelin was well tolerated and safe in normal adults and in advanced cancer patients most of whom were on chemotherapy and/or radiation regimens. It is highly likely to be well tolerated and safe in generally healthy community-dwelling adults in this study.

Placebo The matching placebo tablets will contain the inert substance microcrystalline cellulose that is not expected to have any adverse effect.

Blood draws Expected risks of a blood draw include slight discomfort on puncturing the skin and possible bruising in the area. Uncommon or rare risks may include phlebitis and/or scarring. The amount of blood to be drawn, 9 ml for the screening tests and 56 ml for the intra-study measures is well within the limit for research participants (maximum allowable is 500 ml over 8 weeks according to the American Red Cross).

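### Does asking for the usual dinner before every visit undo the meat-free evening required before the primary-endpoint urine samples?

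*Combined protocol and SAP*

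**What the plan says.** Two parts of the protocol speak to what participants eat on the evening before a visit.

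- **Protection against risks (glucose monitoring).** After setting out how raised fasting glucose will be handled, the paragraph ends: "Subjects will be asked to consume their usual dinner on the evening prior to each study visit". No visit is excepted.
- **F. Measurement procedures, D₃-creatine.** "To minimize variability in this muscle mass measurement, participants will be asked not to eat foods containing creatine or creatinine", glossed as animal products, "after their mid-day meal on the day prior to these urine collections on visits 0 and 12 months". The section adds: "A handout will be provided to guide participants in what they should and should not eat on these two occasions".

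Three other places fix the timing.

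- The D₃-creatine section describes taking the labelled dose "and then providing a fasting morning urine sample" three to six days later.
- Biochemical measurements says: "Blood will be drawn after a 12-hr overnight fast".
- Footnote g of the schedule of activities lists "fasting plasma glucose & serum AST/ALT at 0, 2, 6, and 12 mo". The schedule places the fasting spot urine at 0 and 12 months.

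**The concern.** The general request says each visit and makes no exception. The D₃-creatine request covers the evening meal before two of those visits. Someone who normally eats animal products at dinner would have to break one request to keep the other, and the protocol states no order of precedence.

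The two evenings matter. Muscle mass by D₃-creatine dilution is the primary endpoint, and it is measured only at 0 and 12 months. The plan gives reduced measurement variability as the reason for the restriction. If the general request were followed to the letter, that precaution could lapse for the two samples that make up each participant's change score. In a trial planned around 12 completers per group, extra noise in the primary measurement would be unwelcome.

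**Working it through.** There is no planned figure to reproduce, so the check sets the texts side by side.

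**1. Where the requests meet.**

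| Visit | Fasting glucose | D₃-creatine urine | Usual dinner requested | Animal products restricted |
|---|---|---|---|---|
| 0 | yes | yes | yes | yes |
| 2 mo | yes | no | yes | no |
| 6 mo | yes | no | yes | no |
| 12 mo | yes | yes | yes | yes |

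The overlap is 2 of the 4 fasting-glucose visits and 2 of the 2 urine collections.

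**2. Whether the fast separates them.** It does not. The restriction starts after the mid-day meal and the overnight fast starts after dinner. Dinner lies between the two, and a fast limits when people eat rather than what the meal contains.

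**3. Who is affected.** Only participants whose usual dinner includes the restricted foods. The documents do not say how many that is. Multiplying visits by participants would therefore give a ceiling, not a count of affected samples.

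**4. Whether the requests can be read together.** The usual-dinner sentence stands in a paragraph on glucose. It is naturally read as asking people not to skip or alter a meal before a glucose test. The D₃-creatine request names two visits, a starting time, a reason and a handout for those occasions. A dated, specific instruction ordinarily qualifies a general one. On that reading participants eat dinner as usual before every visit, and on two evenings they leave out animal products.

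**5. Whether the glucose reason falls away at visit 0.** One might argue that it does, because the section on known potential risks says: "To identify intra-study hyperglycemia we will monitor fasting plasma glucose at 2, 6, and 12 months". That does not settle the matter. Footnote g includes month 0 under safety monitoring, and that value is the reference for later ones. The usual-dinner request has a purpose on both evenings, so the overlap cannot be dismissed this way.

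**6. What a lapse would do.** It requires staff to apply the general sentence while overlooking the D₃-creatine section and its handout. Even then the sample would still be a fasting morning one, and the algorithm would still use measured labelled creatinine, unlabelled creatinine and creatine. That does not prove the result is insensitive to diet, since the restricted foods contain two of the substances measured. But the documents give no share of the variance due to the previous dinner, so no change in the planning standard deviation of 1.84 kg can be calculated. Both arms receive the same instructions under randomisation and blinding, which gives no reason to expect a lapse to favour one arm.

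**The case for a change.** The best case for acting is that the contradiction is literal and cheap to remove. Both sentences are requests, so neither outranks the other by its wording. A coordinator drafting visit reminders from the risk section alone would find no exception. The sentence about the handout does not mention the usual-dinner request. The affected samples are the only two behind the primary endpoint, and a clause in one sentence would close the gap. An internal inconsistency about sample collection can be reported without an effect estimate.

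Part of this stands. The wording overlaps, no cross-reference exists, and adding one would be harmless tidying. The step from there to a threat to the primary endpoint does not stand. The handout is the participant-facing instruction for exactly these two evenings. It is not among the documents available, so nobody can say that participants receive conflicting advice. The case also accepts that the D₃-creatine request probably governs in practice and that the effect may be nil.

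**Conclusion.** The inconsistency is real but editorial, and the plan does not need to change on account of it. It covers two evenings per participant, and only for those whose usual dinner contains animal products. No effect on the variability of the D₃-creatine measurement, on power or on the comparison between arms has been shown, and the documents give nothing from which to compute one. A cross-reference would leave the endpoint, schedule, sample size and analysis as they are.

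This rests on two assumptions: that staff work from the whole protocol, including the D₃-creatine section, and that the handout reflects that section as the protocol says it will. Evidence that participants were told to disregard the restriction on either evening would reopen the point. Nothing in the documents suggests that.
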